2 LIST OF ABBREVIATIONS AND DEFINITIONS OF TERMS

Abbreviation	Term
ADA	anti-drug antibody
AE	adverse event
AFP	α -fetoprotein
ATC	anatomical therapeutic chemical
BCLC	Barcelona Clinic Liver Cancer
BLQ	below lower quantification
BMI	body mass index
BOR	best overall response
BW	body weight
CBR	clinical benefit rate
CI	confidence interval
CR	complete response
CRF	case report form
CSR	clinical study report
CTCAE	common toxicity criteria for adverse events
DCR	disease control rate
DLT	dose limiting toxicity
DOE	duration of response
ECG	electrocardiogram
ECOG	Eastern Cooperative Oncology Group
HCC	hepatocellular carcinoma
IV	Intravenous
LLOQ	lower limit of quantification
LLT	lower level term
LVEF	left ventricular ejection fraction
MedDRA	Medical Dictionary for Regulatory Activities
MUGA	multiple-gated acquisition technique
NE	not evaluable
NYHA	New York Heart Association
ORR	objective response rate
OS	overall survival
PD	pharmacodynamics
PD	progressive disease

Abbreviation	Term
PFS	progression free survival
PGx	pharmacogenomics
PK	pharmacokinetics
PR	partial response
PS	performance status
PT	preferred term
QD	every day
QOD	every other day
QTcF	QT interval corrected for heart rate using Fridericia's formula
Q2W	every 2 weeks
RECIST	response evaluation criteria in solid tumor
SAE	serious adverse event
SAP	statistical analysis plan
SD	stable disease
SD	standard deviation
SI	système international
SOC	system organ class
SpO ₂	percutaneous oxygen saturation
TEAE	treatment-emergent adverse event
TE MAV	treatment-emergent markedly abnormal laboratory value
TLG	tables, listings, and graphs
TNM	tumor, nodes, metastasis
TTT	time to progression
TTR	time to response
WHO DD	World Health Organization drug dictionary

3 INTRODUCTION

The purpose of this statistical analysis plan (SAP) is to describe the procedures and the statistical methods that will be used to analyze and report results for Eisai Protocol E7080-J081-117.

3.1 Study Objectives

3.1.1 Primary Objective

- To evaluate the tolerability and safety for combination of lenvatinib plus nivolumab in subjects with hepatocellular carcinoma (HCC)

3.1.2 Secondary Objectives

- To evaluate the following efficacy endpoint based on investigator review in subjects with HCC:
 - Objective response rate (ORR)
- To assess the pharmacokinetic (PK) profile of lenvatinib and nivolumab

3.1.3 Exploratory Objective

3.2 Overall Study Design and Plan

This study will be conducted in 2 parts (Part 1 and Part 2). Part 1 will assess the tolerability of lenvatinib in combination with nivolumab in HCC for which no other appropriate therapy

is available. Part 2 is to further characterize the safety and tolerability and to assess preliminary efficacy of the combination therapy in HCC with no prior systemic therapy.

3.2.1 Part 1

In Part 1, the tolerability review of Cycle 1 (4 weeks) will be conducted by dose limiting toxicities (DLTs). Study treatment and starting dose is as follows:

Lenvatinib: 12 mg (Body Weight [BW] \geq 60 kg) or 8 mg (BW $<$ 60 kg) once daily orally

Nivolumab: 240 mg (every 2 weeks [Q2W], intravenous [IV])

The tolerability will be reviewed based on Dose Limiting Toxicity (DLT) of Cycle 1 (4 weeks) according to the following procedures.

First, 3 subjects will be enrolled.

(1) DLT occurs in 0 or 1 of 3 subjects

Add 3 more subjects and assess in a total of 6 subjects.

1) DLT occurs in 0 or 1 of 6 subjects

This dose level is judged to be tolerable.

2) DLT occurs in 2 or more of 6 subjects

The tolerability with this dose level will be discussed by the sponsor, sponsor's responsible medical officer, and investigators.

(2) DLT occurs in 2 or more of 3 subjects

The tolerability with this dose level and appropriateness of additional enrollment will be discussed by the sponsor, sponsor's responsible medical officer, and investigators.

[figure not shown]
In this dose level, at least 3 subjects treated with lenvatinib 12 mg (BW \geq 60 kg) and nivolumab need to be included in the 6 subjects for DLT evaluation. If this dose level is not tolerable, upon discussions between the sponsor, sponsor's responsible medical officer, and investigators, the lower dose level of cohort will be considered or the study will be discontinued, and the protocol will be amended as necessary. An efficacy and safety evaluation advisor maybe consulted for the consideration as needed.

3.2.2 Part 2

If the dose level is confirmed to be tolerable, an additional 20 HCC subjects with no prior systemic therapy will be enrolled. At least 5 subjects (BW \geq 60 kg) treated with Lenvatinib 12 mg QD and at least 5 subjects (BW $<$ 60 kg) treated with Lenvatinib 8 mg QD will be included.

3.2.3 Study Design

An overview of the study design is presented in Figure 1. Part 1 and Part 2 will consist of a pretreatment period, a treatment period, and a follow-up period.

DLT = dose limiting toxicity.

a: Screening assessment should be performed within 14 days of first dose. (Informed consent can be obtained within 28 days of first dose.)

Figure 1 Study Design

3.2.3.1 Pretreatment Period

The pretreatment period will involve obtaining informed consent, a screening assessment, and a baseline assessment. Screening will occur within 14 days before starting study drug administration after obtaining written informed consent. Informed consent will be obtained after the study has been fully explained to each subject and before the conduct of any screening procedures or assessments (informed consent can be obtained within 28 days of first dose). After screening assessments, the sponsor will be informed of eligibility of the patient by the investigator or subinvestigator. The baseline assessment will be conducted within 4 days before starting study drug administration in order to confirm that the patient meet the eligibility requirement before moving to the Treatment Period.

3.2.3.2 Treatment Period

In the Treatment Period, subjects will receive lenvatinib in combination with nivolumab. The Treatment Period will begin with the first dose of study drug administration on Cycle 1

Day 1. Each cycle is 28 days long and subjects continue treatment until they meet any of the criteria in “Discontinuation Criteria by Subject (see [Protocol Section 9.3.3.1](#))”.

Subjects will be hospitalized during the Cycle 1, however, outpatient is allowed after Cycle 1 Day 15, when investigator or subinvestigator judges that that the subject’s safety is ensured.

3.2.3.3 Follow-up Period

The follow-up period will consist of the examination at study discontinuation and the last observation visit which occurs 30 days after final administration of study drug. If the last observation visit occurs within 7 days after study drug discontinuation, discontinuation data can be used as the last observation data. The subject who discontinues study will have a discontinuation visit and last observation which occurs 30 days after final administration of study drug. If a new anticancer agent needs to be immediately started due to deterioration in the subject’s condition, the final observation visit can be conducted before 30 days after the last dose of the study drug has passed but prior to starting the new anticancer agent.

In Part 2, all subjects will be followed for survival until death every 12 weeks (± 2 week) from the date of discontinuation, except where a subject withdraws consent or the sponsor chooses to halt survival follow-up. The survival follow-up will be continued for up to 2 years after Cycle 1 Day 1 of the last subject enrolled in Part 2.

4 DETERMINATION OF SAMPLE SIZE

A sample size of approximately 26 subjects will be enrolled in this study, 6 subjects for Part 1 and 20 patients for Part 2. Six subjects in Part 1 was deemed appropriate to evaluate the tolerability of the dose and perform preliminary safety assessment. Twenty subjects in Part 2 was determined to further evaluate the safety and preliminary efficacy. The probability to detect at least 1 development of intolerable treatment-related AEs with a true incidence of 10%, 15% or 20% in 20 subjects was 87.8%, 96.1%, or 98.8%, respectively. Therefore, the sample size is determined to be approximately 20 subjects.

5 STATISTICAL METHODS

All statistical analyses will be performed by the sponsor or designee after the data cutoff for analysis or the study is completed and the database is locked. Statistical analyses will be performed using SAS software or other validated statistical software as required.

All descriptive statistics for continuous variables will be reported using mean, standard deviation (SD), median, minimum and maximum. Categorical variables will be summarized as number (percentage) of subjects.

All statistical analysis will be performed by part separately. Summarization for lenvatinib 8 mg group, 12 mg group and total subjects will be presented.

5.1 Study Endpoints

The endpoints of this study are shown below. All efficacy endpoints will be assessed using mRECIST. If necessary, RECIST1.1 will also be performed and used for analysis.

5.1.1 Primary Endpoints

- DLTs (Part 1 only)
- Safety endpoints including AEs, laboratory tests, vital signs, ECG, ECOG-PS, and LVEF

5.1.2 Secondary Endpoints

- **ORR** is defined as the proportion of subjects who have BOR of CR or PR
- Pharmacokinetic parameters of lenvatinib

5.1.2.1 Pharmacokinetic (PK) Endpoints

PK parameters derived by non-compartmental analysis using plasma concentrations of lenvatinib (Part 1) which include, but are not limited to, are shown as below:

C_{\max}	maximum observed concentration
t_{\max}	time at which the highest drug concentration occurs
$AUC_{(0-t)}$	area under the concentration-time curve from zero time to time of last quantifiable concentration
$AUC_{(0-\infty)}$	area under the concentration-time curve from zero time extrapolated to infinite time
$t_{1/2}$	terminal elimination phase half-life
CL/F	apparent total clearance following oral dosing
V_z/F	apparent volume of distribution at terminal phase

MRT	mean residence time
$C_{ss,max}$	maximum observed concentration at steady state
$C_{ss,min}$	minimum observed concentration at steady state
$t_{ss,max}$	time at which the highest drug concentration occurs at steady state
$AUC_{(0-\tau)}$	area under the concentration-time curve over the dosing interval
CL_{ss}/F	apparent total clearance following oral administration at steady state
$C_{ss,av}$	average steady-state concentration
$R_{ac}(C_{max})$, $R_{ac}(AUC)$	accumulation index
PTF ratio	peak-trough fluctuation ratio

5.1.3 Exploratory Endpoints

CCI

CCI

5.2 Study Subjects

5.2.1 Definitions of Analysis Sets

DLT Analysis Set will include all subjects (Part 1 only) who have completed Cycle 1 without major protocol deviation with at least 75% of lenvatinib compliance and at least 2 doses of nivolumab and are assessed for DLT, or subjects who have experienced DLT during Cycle 1. This will be the analysis set to determine tolerability.

Safety Analysis Set will include all subjects who received at least 1 dose of lenvatinib or nivolumab.

PK Analysis Set for Lenvatinib will include all subjects who have received at least 1 dose of lenvatinib and nivolumab, and have evaluable concentration data of lenvatinib.

PK Analysis Set for Nivolumab will include all subjects who have received at least 1 dose of lenvatinib and nivolumab, and have evaluable concentration data of nivolumab.

The Efficacy Analysis Set will include all subjects who received at least 1 dose of lenvatinib and nivolumab.

The Pharmacodynamic and PGx Analysis Set is the group of subjects who received at least 1 dose of lenvatinib and nivolumab and had at least 1 postdose pharmacodynamic or PGx data.

The number of subjects enrolled (ie, subjects who signed informed consent), the number (percentage) of subjects included in each analysis set will be presented. Subject data listings will be provided.

5.2.2 Subject Disposition

For the summary table of screening subjects, the number (percentage) of subjects who were enrolled, continued in the study after screening, failed screening, and the primary reason for screen failures will be presented.

For the summary of the subject disposition, the number (percentage) of subjects who were treated/not treated, completed/discontinued the study, and the reason for the study discontinuation will be presented. Similarly, the number (percentage) of subjects who completed/discontinued the study treatment, and the reason for the discontinuation from study treatment will also be summarized. The number (percentage) of subjects who discontinued either lenvatinib alone or nivolumab alone and the reason for discontinuation will be summarized.

In this protocol, subjects who completed the study are defined as subjects who completed the appropriate DLT evaluation in Part 1, or subjects who completed the discontinuation assessment or last observation assessment in Part 2. Subjects who completed the study treatment are defined as who discontinued the treatment due to disease progression or subjects who are continuing the study treatment at the date of data cutoff.

Subject data listings will be provided.

5.2.3 Protocol Deviations

Important protocol deviation criteria will be established and subjects with important protocol deviations will be identified and documented before the database lock. Also, protocol deviations related to COVID-19 (coronavirus disease 2019) and subjects with the deviations will be identified and documented before database lock.

Subject data listings will be provided.

5.2.4 Demographic and Other Baseline Characteristics

Demographic and other baseline characteristics will be summarized using descriptive statistics in Safety Analysis Set.

Continuous demographic and baseline variables include

- Age
- Height
- Weight
- BMI

Categorical demographic and baseline variables include

- Age group (< 65 years, \geq 65 to < 75 years, \geq 75 years)
- Weight group (< 60kg, \geq 60 kg)
- Sex
- Race
- Ethnicity
- ECOG-PS
- NYHA (I, II, III, IV and NA for Heart failure)

Disease history and characteristics at study entry will also be summarized by:

- HCC type (Fibrolamellar, Scirrhous, Spindle cell variant, Pleomorphic type, Clear cell type, Trabecular, Multinodular differentiated, Moderately differentiated, Poorly differentiated, Well differentiated, Biopsy performed – HCC type unknown, Biopsy not performed, Other)
- Child-Pugh score

- BCLC stage
- AFP (as continuous variable)
- AFP group (<200 ng/mL, \geq 200 ng/mL)
- Macroscopic portal vein invasion (Yes, No)
- Portal vein involvement (Vp0, Vp1, Vp2, Vp3, Vp4)
- Extrahepatic spread (Yes, No)
- Involved disease organ
- Number of involved disease organ per patient (1, 2, \geq 3)
- Diagnosis of HCC (Histological or cytological diagnosis of HCC, Clinically confirmed diagnosis of HCC)
- Time from confirmed diagnosis of HCC to the date of first study treatment (months) (as continuous variable)
 - For patients who were “histologically or cytologically” and “clinically” confirmed, whichever earlier diagnosis date is used.
- TNM classification at diagnosis
- Tumor staging at diagnosis
- Factor of Carcinogenesis (Hepatitis B, Hepatitis C, Alcohol, Unknown, Other)
- Number of previous anticancer medication as regimen (0, 1, 2, \geq 3)
- Subjects with any previous radiotherapy

Previous anticancer procedure will be summarized by:

- Subjects with any previous anticancer procedure
- Number of previous anticancer procedure (0, 1, 2, 3, 4, \geq 5)
- Previous procedure name (Hepatic intra-arterial chemotherapy, Transarterial [chemo] embolization, Radiofrequency ablation, Cryoablation, Percutaneous ethanol injection, Hepatectomy, Other)
- Time from end of most recent procedure to the date of first study treatment (months) (as continuous variable)

Subject data listings will be provided.

Medical History

A subject data listing of medical history and current medical condition will be provided.

5.2.5 Prior and Concomitant Therapy

All investigator terms for medications recorded in the CRF will be coded to an 11-digit code using the World Health Organization Drug Dictionary (WHO DD) drug codes. Prior medications will be defined as medications that started before the first dose of study treatment. Concomitant medications will be defined as medications that (1) started before the first dose

of study treatment and were continuing at the time of the first dose of study drug, or (2) started on or after the date of the first dose of study treatment up to 30 days after the subject's last dose. Medications received after 30 days of last dose will be considered as post treatment medications.

The number (percentage) of subjects who took prior and concomitant medications will be summarized by Anatomical Therapeutic Chemical (ATC) class (anatomical class, pharmacological class), and WHO DD preferred term on the Safety Analysis Set.

Non-pharmacological procedures will be classified into standardized medical terminology using the Medical Dictionary for Regulatory Activities (MedDRA version 20.1 or later).

All medications and non-pharmacological procedures will be presented in subject data listings.

5.2.6 Treatment Compliance

Treatment related protocol deviations will be presented in CSR as provided in the [section 5.2.3](#).

5.3 Data Analysis General Considerations

5.3.1 Pooling of Centers

Subjects from all centers will be pooled for all analyses.

5.3.2 Adjustments for Covariates

No adjustment for covariates will be performed.

5.3.3 Multiple Comparisons/Multiplicity

No statistical comparison is planned in this study.

5.3.4 Examination of Subgroups

No subgroup analysis will be performed.

5.3.5 Handling of Missing Data, Dropouts, and Outliers

The details of handling of missing data will be described in the [section 8](#).

5.3.6 Other Considerations

Not applicable.

5.4 Efficacy Analyses

Efficacy analyses will be conducted on the Efficacy Analysis Set. Tumor assessment will be analyzed base on the investigator's assessment. If needed, the analysis based on independent review will be conducted.

5.4.1 Efficacy Analyses

Part 1

BOR will be summarized based on mRECIST, and ORR and its corresponding exact 2-sided 95% confidence interval (CI) will be calculated. DCR and CBR will be summarized in a same manner.

Part 2

In addition to the same analysis as above for Part 1, following analyses will be performed.

PFS is defined as the time from the date of first dose to the date of first documented PD or death due to any cause (whichever occurs first) and calculated as below. For subjects who do not have an event, PFS will be censored. Censoring rules for PFS are shown in [Table 1](#) Censoring rules for PFS.

$$\text{PFS (months)} = (\text{Date of first documented PD/ death/ censored date} - \text{Date of first dose} + 1) / (365.25/12).$$

The PFS rate will be calculated using Kaplan-Meier method. The median, Q1, and Q3 for PFS with their 95% CIs will be evaluated. The 95% CIs will be calculated based on Greenwood formula and a generalized Brookmeyer and Crowley method with log-log transformation. The number (percentage) of subjects with event/censored will be summarized. The PFS rate with its 95% CI at 2, 4, 6, 8, 10 and 12 months will also be calculated, but not limited to these time points. Kaplan-Meier plots with the number of subjects at risk will be presented.

TTP is defined as the time from the date of first dose to the date of first documented PD and calculated as below. For subjects who do not have an event, TTP will be censored. Censoring rules for TTP are shown in [Table 2](#) Censoring rules for TTP. TTP will also be summarized in the same manner as with PFS.

$$\text{TTP (months)} = (\text{Date of first documented PD/ censored date} - \text{Date of first dose} + 1) / (365.25/12).$$

DOT is defined as the time from the first documentation of CR or PR to the date of first documented PD or death (whichever occurs first) and calculated as below. DOT will be

calculated only for subjects having at least one CR or PR. Censoring rules for DOR is same as PFS. DOR will also be summarized in the same manner as with PFS.

DOR (months) = (Date of first documented PD/ death/ censored date – Date of the first documentation of CR or PR + 1) / (365.25/12).

TTR is defined as the time from the date of first study dose to the date of first documentation of CR or PR and calculated as below. TTR will be summarized in only subjects with CR or PR using summary statistics.

TTR (months) = (Date of documentation of CR or PR – Date of first dose + 1) / (365.25/12).

OS is defined as the time from the date of first study dose to the date of death due to any cause and calculated as below. Subjects who are lost to follow-up and the subjects who are alive at the date of data cutoff will be censored at the date the subject was last known alive or the cut-off date, whichever comes earlier. Censoring rules for OS are shown in [Table 3](#)
Censoring rules for OS. OS will also be summarized in the same manner as with PFS.

OS (months) = (Date of death/ censored date – Date of first dose + 1) / (365.25/12).

A waterfall plot will be presented for the percent changes from baseline in the sum of the diameters of target lesions at post-baseline nadir (ie, maximum tumor shrinkage). A spider plot will be presented for the percent changes from baseline in the sum of the diameters of target lesions. The diameters after subsequent anti-cancer treatment initiation are not included in the waterfall and spider plot.

Summary statistics for tumor marker (AFP) the changes and percent changes from baseline will be presented by visit. Also, AFP will be categorized as >200 µg/L or <= 200 µg/L and presented by visit.

Subject data listings will be provided.

Table 1 Censoring rules for PFS

No.	Situation	Date of Event or Censoring	Outcome
1	No baseline tumor assessments	Date of first dose	Censored
2	Progression documented at scheduled visit	Date of first radiologic PD assessment	Event
3	Progression documented between scheduled visits	Date of first radiologic PD assessment	Event
4	No progression nor death at the time of data cut-off or discontinuation from study treatment	Date of last adequate radiologic assessment*	Censored
5	New anticancer treatment started	Date of last adequate radiologic assessment* prior to or on date of new anticancer treatment	Censored
6	Death before first PD assessment	Date of death	Event
7	Death between adequate assessment visits*	Date of death	Event
8	Death or progression after two or more consecutive missed visit/tumor assessment**	Date of last adequate radiologic assessment* before missed tumor assessments	Censored

* Adequate tumor assessment is a radiologic assessment of CR, PR, SD, non-CR/non-PD or PD as determined by investigators.

** More than one missed visit is defined if the duration between the last tumor assessment and death or PD is longer than 126 days (ie. 8 weeks x 2 + 2 weeks [allowance of visit]) for subjects on the every 8 week scanning schedule in this study.

The priority of the censoring rules is as follows:

1. If the subject had PD or death, the following sequence will be applied:

- If a subject did not have baseline tumor assessment (No. 1), the subject will be censored on date of first dose. However, if the subject died within 56 days (8 weeks) after the first dosing date and did not receive new anticancer treatment, the date of death will be the PFS event date (not censored).
- If a subject had new anticancer treatment before PD or death (No. 5), the subject will be censored on the date of the last adequate tumor assessment prior to or on the date of new anticancer treatment.
- If a subject missed two or more assessments consecutively before PD or death (No. 8), the subject will be censored on the date of the last adequate tumor assessment before PD or death. Note that if a subject is censored by both this criterion and the anticancer treatment criteria, the earliest censoring date will be used.
- Otherwise, if a subject had an event (No. 2, 3, 6, 7), the earliest event date will be used.

2. If a subject did not have PD or death, the censoring date will be the earliest censoring date if the subject met multiple censoring criteria (No. 1, 4, 5, 8).

Table 2 Censoring rules for TTP

No.	Situation	Date of Event or Censoring	Outcome
1	No baseline tumor assessments	Date of first dose	Censored
2	Progression documented at scheduled visit	Date of first radiologic PD assessment	Event
3	Progression documented between scheduled visits	Date of first radiologic PD assessment	Event
4	No progression at the time of data cut-off or discontinuation from study treatment	Date of last adequate radiologic assessment*	Censored
5	New anticancer treatment started	Date of last adequate radiologic assessment* prior to or on date of new anticancer treatment	Censored
6	Death before first PD assessment	Date of last adequate radiologic assessment*	Censored
7	Death between adequate assessment visits*	Date of last adequate radiologic assessment*	Censored
8	PD after two or more consecutive missed visit/tumor assessment**	Date of last adequate radiologic assessment* before missed tumor assessments	Censored

* Adequate tumor assessment is a radiologic assessment of CR, PR, SD, non-CR/non-PD or PD as determined by investigators.

** More than one missed visit is defined if the duration between the last tumor assessment and PD is longer than 126 days (ie. 8 weeks x 2 + 2 weeks [allowance of visit]) for subjects on the every 8 week scanning schedule in this study.

The priority of the censoring rules is as follows:

1. If the subject had PD, the following sequence will be applied:

- If a subject did not have baseline tumor assessment (No. 1), the subject will be censored on date of first dose.
- If a subject had new anticancer treatment before PD (No. 5), the subject will be censored on the date of the last adequate tumor assessment prior to or on the date of new anticancer treatment.
- If a subject missed two or more assessments consecutively before PD (No. 8), the subject will be censored on the date of the last adequate tumor assessment before PD.
- Otherwise, if a subject had an event (No. 2, 3), the earliest event date will be used.

2. If a subject did not have PD, the censoring date will be the earliest censoring date if the subject met multiple censoring criteria (No. 1, 4, 5, 6, 7, 8).

Table 3 Censoring rules for OS

No.	Situation	Date of Event or Censoring	Outcome
1	Death before or on data cut off	Date of Death	Event
2	Death after data cut off	Date of data cut off	Censored
3	Subject still alive at data cut off	Date of data cut off	Censored
4	Subject lost to follow-up or withdraw of consent before data cut off	Date last known to be alive	Censored

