9.5.1.3 Efficacy Assessments

9.5.1.3.1 TUMOR ASSESSMENTS

All efficacy endpoints will be based on tumor assessments performed by the investigators using mRECIST (Appendix 2). If necessary, independent review using mRECIST and RECIST1.1 will be performed (Part 2 only).

Tumor assessments will be carried out at Screening and then every 8 weeks (Day 1 [± 7 days] in odd number cycle) from Day 1 of Cycle 1, or more frequently if disease progression is clinically indicated. Historical standard of care scans that are performed with scanning parameters consistent with the requirements for this protocol within 28 days prior to dosing are acceptable (scans before informed consent can be acceptable).

Screening tumor assessments using triphasic liver CT/MRI (optimized for pre-contrast, arterial, and portal venous phase), contrast-enhanced CT of the chest, and contrast-enhanced CT or MRI of abdomen, pelvis, and other areas of known disease plus suspected disease should be performed within 28 days prior to C1D1. CT or MRI will be performed using contrast media unless there is an allergy to contrast media. If there is known allergy to contrast media, non-contrast CT or MRI will be used.

Screening CT of the brain with contrast or MRI of the brain pre- and post-gadolinium should be performed within 28 days prior to C1D1. During the Treatment Phase, CT/MRI of the brain should be performed if clinically indicated. The same methodology and scan acquisition techniques used at Screening should be used throughout the study to ensure comparability.

During the Treatment Phase, tumor assessments of the chest, abdomen, pelvis, and other areas of known disease at Screening plus newly suspected disease should be performed every 8 weeks (Day 1 [± 7 days] in odd number cycle) or more frequently, if clinically indicated. The same methodology (CT or MRI) and scan acquisition techniques including use and timing of IV contrast should be used as for the screening assessments. Tumor assessment at the discontinuation visit is only necessary if more than 4 weeks have passed since the

previous assessment (window for these assessments is within 1 week of discontinuation visit).

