8.2 Efficacy Data Handling

Handling of missing data for tumor assessment result

For the analysis of ORR, DCR and CBR, subjects with missing response status (subjects whose baseline is missing and/or no adequate post-baseline tumor assessments result) will be coded as non-responders on Efficacy Analysis Set.

Data of tumor assessment result after documented PD or discontinuation from treatment

For the analysis of tumor assessment relevant efficacy endpoints, tumor assessment result after PD or final observation visit (for non-PD patients) are excluded from the analyses, but included in subject data listing.

Visit Windows

The purpose of visit windows is to provide a single record per subject per visit for the calculation of descriptive statistics for tumor marker per scheduled visit, and change from baseline per visit.

The observation closest to the target date will be used in by visit summaries. If two or more observations have the same distance to the target visit day, the one that has the highest value will be used for summary tables. If the multiple data in the same distance to the target date are same, the data measured at an earlier date will be used for summary tables.

The visit window is applied for tumor marker assessment summary.

Analysis visit	Target Day	Analysis Window	
		Start Day	End Day
Cycle 3 Day 1	Cycle 3 Day 1	Cycle 3 Day 1 - 7	Cycle 3 Day 1 + 7
Cycle 5 Day 1	Cycle 5 Day 1	Cycle 5 Day 1 - 7	Cycle 5 Day 1 + 7
Cycle n Day 1 (n ≥ 7 and odd numbers)	Cycle n Day 1	Cycle n Day 1 - 7	Cycle n Day 1 + 7

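### The PFS and TTP censoring tables give no usable date for a treated subject without an adequate post-baseline scan, and the 126-day clock can start at the screening scan

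*SAP*

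**What the plan says.** SAP 5.4.1, Table 1 (PFS), has eight situations:

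- Row 1 covers a missing baseline assessment: censored at first dose, with an exception in the priority list for a death within 56 days without new anticancer treatment.
- Rows 4, 5 and 8 censor at the last adequate radiologic assessment. The footnote defines this: "Adequate tumor assessment is a radiologic assessment of CR, PR, SD, non-CR/non-PD or PD as determined by investigators".
- Row 6, "Death before first PD assessment", is an event at the date of death.
- Row 8 censors a death or progression that follows two or more consecutive missed assessments. Its footnote says: "More than one missed visit is defined if the duration between the last tumor assessment and death or PD is longer than 126 days". The limit is built as two 8-week intervals plus 2 weeks of visit allowance.
- The priority list applies rows 1, 5 and 8 before the event rows 2, 3, 6 and 7.

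Table 2 (TTP) has the same structure, except that deaths (rows 6 and 7) are also censored at the last adequate assessment. Both SAP versions in the file carry these PFS and TTP rules.

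Protocol 9.5.1.3.1 says: "Tumor assessments will be carried out at Screening and then every 8 weeks". Of the screening scan it says that it "should be performed within 28 days prior to C1D1".

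SAP 8.2 does recognise the case at issue, "subjects whose baseline is missing and/or no adequate post-baseline tumor assessments result", but only for ORR, DCR and CBR, where it means non-responder.

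**The concern.** Take a subject who received both drugs, had the screening scan and never had an evaluable scan afterwards. The Efficacy Analysis Set keeps this subject, because it requires only one dose of each drug. Two things then go wrong in Tables 1 and 2.

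First, the date is missing. A screening scan carries no response category, so it is not an adequate assessment under the footnote. If the subject is alive without progression (row 4), starts new treatment (row 5) or falls under row 8, the tables point to a date that does not exist. TTP is affected more widely, because its rows 6 and 7 also send deaths to that date.

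Second, the missed-scan clock has a doubtful start. The footnote counts from the last tumor assessment and does not say adequate or post-baseline. The protocol treats the screening scan as a tumor assessment, so on the wording it is this subject's last one. The 126 days are meant to stand for two missed scans, but part of that time can elapse before treatment begins. A death that row 6 counts as an event can then be censored by row 8.

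At stake is whether an early death counts in a 20-subject PFS curve, and whether the programmer has to invent a censoring date.

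**Working it through.** **Inputs**

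- Limit: longer than 126 days (SAP Table 1 footnote).
- Screening scan: s days before first dose, with s at most 28 (protocol 9.5.1.3.1). The screening column of protocol Table 9 is Day -14 to -4, but its footnote accepts scans within 28 days.
- Day 1 is the first dose. On-study scans fall on Day 1 of odd cycles, within 7 days either side.
- Discontinuation scan: needed only if more than 4 weeks have passed since the previous one (protocol 9.5.1.3.1).
- Planned Part 2 size: 20.

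**1. The plan's limit.** 2 × 56 + 14 = 126 days. It reproduces.

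**2. Scan dates.** C3D1 is 28 × 2 + 1 = Day 57, window Days 50 to 64. C5D1 is 28 × 4 + 1 = Day 113, window Days 106 to 120.

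**3. First death affected on the literal reading.** A death on Day D falls (D − 1) + s days after the scan. Row 8 applies when this exceeds 126, so the first affected day is 128 − s. Check at s = 28: Day 99 gives 98 + 28 = 126, not longer than the limit, so still a row 6 event. Day 100 gives 99 + 28 = 127, so row 8 applies.

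| Scan, days before first dose | First affected day | State of the schedule |
|---|---|---|
| 28 | 100 | only C3D1 has fallen due |
| 23 | 105 | only C3D1 has fallen due |
| 22 | 106 | C5D1 window opens |
| 14 | 114 | one day after the C5D1 target |
| 4 | 124 | C5D1 window closed |
| 1 | 127 | C5D1 window closed |

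The rule can therefore declare two missed scans when one was due only if s is at least 23. Counted from first dose, D − 1 > 126 gives Day 128, after both windows have closed.

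**4. Can the case arise without a protocol deviation?** At a discontinuation visit on Day D, no scan is required if (D − 1) + s ≤ 28, that is D ≤ 29 − s. With s = 10 and a stop on Day 15, the gap is 14 + 10 = 24 days, so none is required and the subject may have no post-baseline reading. With s = 28 the exemption covers Day 1 only, and with s = 23 it ends at Day 6. The missing date can thus arise in full compliance. The Day 100 case will nearly always need a required scan that was missed or unreadable.

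**5. Size of one misclassified death.** Assume n = 20, k other events by 4 months, no other censoring, and censoring at Day 1 (an assumption, since the SAP gives no date). Four months is 4 × 365.25/12 = 121.75 days, so a death up to Day 121 counts in the planned 4-month estimate. As an event, 4-month PFS is (19 − k)/20; as censored, (19 − k)/19.

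| k | Event | Censored | Difference |
|---|---|---|---|
| 0 | 95.0% | 100.0% | 5.0 points |
| 2 | 85.0% | 89.5% | 4.5 points |
| 4 | 75.0% | 78.9% | 3.9 points |
| 6 | 65.0% | 68.4% | 3.4 points |

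**The case against.** The strongest reply is that the protocol largely closes the case. A discontinuation scan is required once more than 4 weeks have passed, so most early leavers will have a post-baseline reading, and those exempt have recent screening scans for which the clock expires late. That stands, and it keeps the point small.

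The row 6 and row 8 conflict also depends on reading the footnote literally. Row 8 itself refers to the last adequate assessment. If the clock starts there, this subject has no start date, row 8 cannot apply, and the death stays a row 6 event. The SAP does not say which is meant. The missing date in rows 4 and 5, and throughout TTP, remains on either reading.

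Four stronger inferences are not supported:

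- That early toxicity drop-outs who die are in general removed from the PFS events. Without new anticancer treatment, every such death through Day 99 stays a row 6 event on any reading, given a scan within the permitted 28 days.
- That Day 100 is typical. It is the extreme of the range.
- That PFS times would come out negative. This requires the screening scan to serve as an adequate assessment, which the footnote's definition excludes.
- That row 1 is empty because eligibility requires a measurable lesion. Protocol 9.3.3.1 foresees eligibility violations found after enrollment, and the Efficacy Analysis Set keeps all subjects given both drugs, so row 1 is a legitimate safeguard.

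Finally, SAP section 9 leaves derivation rules to separate documents not available here, which may already settle the date. The tables should still state it.

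**Conclusion.** The point holds as a minor but real defect in the censoring rules. Tables 1 and 2 define no date for a subject with a baseline scan and no adequate post-baseline assessment. On the literal wording, row 8 can also override row 6 from Day 128 − s, which is Day 100 to Day 127 for scans 28 days to 1 day before dosing. It can do so before a second on-study scan has fallen due only when the scan was at least 23 days before dosing.

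Few subjects are likely to be affected; the documents support no frequency. PFS is a descriptive Part 2 analysis, neither a primary nor a secondary endpoint, and no statistical comparison is planned. Each subject is nonetheless 1/20 = 5% of Part 2, and under the stated assumptions one reclassified death moves 4-month PFS by 3.4 to 5.0 points. The timing result assumes the literal reading of the footnote. The missing-date result does not.

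**What to change.** Three edits to SAP 5.4.1, best made together:

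1. In the 126-day footnotes of Tables 1 and 2, measure from the later of the first dose date and the last adequate post-baseline assessment. With no post-baseline reading, the rule then first applies on Day 128 whatever the scan date. For a scan 28 days before dosing, deaths on Days 100 to 127 return to row 6.
2. State that where no adequate post-baseline assessment exists, the censoring date in PFS rows 4, 5 and 8 and TTP rows 4 to 8 is the date of first dose.
3. Leave row 1 and its 56-day exception for a missing baseline only. Adding these subjects to row 1 looks simpler, but row 1 comes first in the priority list, so their deaths after 56 days would be censored at first dose. Kept separate, deaths without a post-baseline scan remain row 6 events up to the 126-day limit, unless new anticancer treatment came first.

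One side effect should be confirmed as intended: with adequate in the footnote, a scan read as not evaluable no longer restarts the clock.

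The cost is a few sentences of SAP text and a matching check of the programming specifications before database lock. No data collection or design change is needed.
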